### 3.6.2 Unblinding Procedure

It is the intention of this study to unblind both the subject and the site study personnel at the completion of the study. This will occur **after** all necessary 30-day follow-up assessments are completed and all the data have been collected and verified.

If the subject develops a condition within the 30-day follow-up window, the subject and team will be unblinded only if doing so is necessary to make informed decisions about clinical care. To the extent possible, the surgical team will remain blinded throughout the duration of the study.

Any subject that is unblinded prematurely for any reason shall continue to be followed in accordance with the protocol evaluations outlined. A subject is NOT automatically considered to be withdrawn if unblinding occurs earlier than anticipated.

If the site believes there is reason to unblind either themselves or the subject (significant change in subject's health status related to the possible use of the device, withdrawal or discontinuation of study participation), the site will contact the Sponsor to discuss the subject's circumstances, at which time the Sponsor, if in agreement with the site's request, will approve release of the blinding information by the unblinded Sponsor designee.

### 4. STUDY JUSTIFICATION

Cardiac surgery requiring cardiopulmonary bypass (CPB) has been in clinical practice for over 50 years. This procedure has been lifesaving by allowing many complex cardiac surgical procedures to take place safely. Despite advances however, CPB still frequently evokes inflammatory reactions that lead to postoperative morbidity, organ dysfunction and worsening of renal function. The inflammatory reaction underlying the pathophysiology of these conditions originates from exposure of blood to CPB surfaces during surgery with initiation of the early phase inflammatory response via contact activation. Two specific complications associated with inflammation arising from CPB that pose significant clinical burden in post-operative patient care are the risk of worsening renal function following cardiac surgery and the potential for hemodynamic instability (vasoplegia).

Worsening renal function following cardiovascular surgery is a frequent complication and is associated with significant patient morbidity, complication of post-operative management and mortality. Its severity and chronicity have most commonly been assessed using definitions of Acute Kidney Injury (AKI) and Chronic Kidney Disease (CKD) (Kidney Disease: Improving Global Outcome group - KDIGO 2012). A retrospective examination of in-hospital mortality and length of hospital stay (LOS) in 39,369 broad surgical patients showed that AKI was associated with a fivefold higher mortality and five days longer LOS. AKI is a common post-operative complication occurring in 5-30% of patients following cardiac surgery, and is associated with a more complicated clinical course and with an excessive mortality of up to  $80\%^{27}$ . The long-term mortality risks associated with AKI after cardiac surgery remain high for 10 years after the procedure, irrespective of other risk factors, even in patients that showed complete renal recovery. However, patients not meeting the formal definition of AKI may have already suffered a substantial loss of renal functional reserve; even minimal increases in serum creatinine in the immediate post-operative period >0.0 relative to a patient's pre-operative baseline value are associated with significantly increased mortality and provide an independent risk factor in predicting outcome after cardiac surgery. Ishani et al linked the magnitude of sCr increase post cardiac surgery to increasing rates of CKD, progression of kidney disease and death. Importantly, even minimal increases in sCr were associated with adverse long-term outcomes. Duque-Sosa assessed changes in creatinine as *percent* increase from baseline to peak creatinine levels after cardiac surgery [none (<0%), class I (1%-24%), Class II (25%-49%), Class III (50%99%), or Class IV (>100%)]. This is consistent with the observation of an independent association between even mild AKI and increased morbidity and mortality. Thus, avoiding the development of the initial injury represents a clinically important objective and while the origins of worsening renal function are multifactorial, significant contributors include the increases in levels of inflammatory cytokines and circulatory pfHb.

Vasoplegic Syndrome is characterized by "severe persistent low systemic vascular resistance, hypotension, decreased filling pressure, normal or elevated cardiac output, and tachycardia". CPB induced inflammation is associated with activation of the complement alternative pathway and this can lead to organ dysfunction and vasoplegic syndrome. This amplification of the inflammatory cascade is considered directly associated with the incidence of vasoplegia commonly occurring during CPB along with the SIRS, leading to significant increases in tumor necrosis factor alpha (TNF- $\alpha$ ) and IL-6, pro-inflammatory cytokines, has been observed in some patients undergoing CABG with CPB and may play a significant role in vasoplegia.

Mitigation of the deleterious effects of renal injury therefore requires a multimodal strategy aimed at decreasing factors likely to exacerbate tissue injury during the period of heightened risk, i.e., during CPB.

Two well characterized etiologies of worsening renal function are the generation of pfHb and activated complement during CPB. The extent of hemolysis during CPB surgery is directly correlated with both the length of the CPB procedure (> 3 hours) and the complexity of cardiac

surgery. Red blood cells (RBCs) can hemolyze during CPB due to factors such as negative pressure cardiotomy suction, blood to material interactions, increases in foreign surface to-blood volume ratios, shear stress due to high flow rates through artificial blood circuits, and others.

Hemoglobin is thought to induce worsening renal function through: (a) tubular obstruction caused by heme protein precipitation, (b) ischemic injury resulting from increased renal vascular resistance and vasoconstriction, and (c) heme iron-driven oxidative injury, leading to inflammation and endothelial, tissue, and organ injury. This promotes a pro-inflammatory cascade involving activation, generation, or expression of thrombin, complement, neutrophils, celladhesion molecules, mast cells, and multiple inflammatory mediators and includes the release of cytokines, IL-1 $\beta$ , IL-6, IL-8, and TNF- $\alpha$  5,. Plasma free hemoglobin also accounts for a significant portion of the damaging oxidative stress response that can damage other organs following cardiac surgery. By directly causing tissue injury, in the post-operative SIRS response and through adverse physiologic changes, pfHb is thought to be a significant contributor in the development of multiple organ dysfunction syndrome (MODS) and multiple organ failure (MOF) in many patients following cardiac surgery.

Complement activation within the injured kidney is a proximal trigger of many downstream inflammatory events within the renal parenchyma that exacerbate injury to the kidney. Targeted complement inhibition has become a potential strategy for preventing renal ischemia-reperfusion injury, end-organ damage and fibrosis in surgery and hemodialysis with both clinical and preclinical models suggesting that expression of C3aR and C5aR on both renal and circulating leukocytes contributes to the pathogenesis of renal ischemia-reperfusion injury, as well as a role for C3a and C5a in contributing to the pathogenesis of renal ischemia reperfusion.

Given that pfHb is a known offender causing organ damage in both kidneys and lungs, data suggestive of organ function preservation by intraoperative use of CytoSorb® would be of potential clinical benefit post cardiac surgery. It has been demonstrated in published studies that the risk of AKI increases with the length of CPB and that post-procedure AKI is associated with increases in pfHb (Billings 2016; Windsant 2010). As discussed earlier, AKI was based solely on the serum creatinine criteria. While none of the resulting Odds Ratios (OR) for developing AKI are significantly different from 1, the observed OR (0.260) for patients with a valve replacement suggests there may be a benefit associated with CytoSorb® treatment. This could be the result of the lower increase in pfHb during CPB observed for the valve replacement patients in REFRESH I. Other studies have shown a direct link between development of AKI and chronic kidney disease (CKD) which is independently associated with higher mortality.

Plasma free hemoglobin also accounts for a significant portion of the damaging oxidative stress response that can damage other organs following cardiac surgery. These complications may require increased length of stay and ICU time, prolonged mechanical ventilation, increased risk of nosocomial infections, or may increase the risk for systemic inflammatory response syndrome (SIRS) and potential progression to organ failure. Because of this, the removal of free

hemoglobin during CPB has the potential to significantly reduce the risk of hemolysis-induced organ injury.

Furthermore, the REFRESH I study (see Investigator Brochure) showed that there was a trend for an increased risk of AKI associated with larger increases in TIMP-2 x IGFBP-7 from baseline (p=0.5822). It has been shown that Urine TIMP-2 x IGFBP-7 [(ng/mL)/1000] is associated with the incidence of AKI. A greater increase in Urine TIMP-2/creatinine ratio was seen in the Control arm compared to the Treatment arm suggestive of a possible protective effect of treatment with CytoSorb®. A recent study demonstrated that significantly (p<0.001) higher levels of these markers were observed 4 hours after ICU admission in patients who developed AKI than those whom did not develop AKI. These markers remained flat or decreased in patients without AKI, and started to elevate by the time of ICU admission in those that developed AKI. A reduction in pfHb and other inflammatory mediators could potentially be another mechanism by which CytoSorb® could decrease the risk of AKI in post cardiac surgery patients.

Consistent with the effect of device, treatment in the REFRESH I study (see Investigator Brochure) also showed a strong trend in decreasing activated complement C3a and C5a during surgery as well as other inflammatory markers. This trend was shown in a previous CytoSorb® study by Born in 2014. Research has shown that the complement system has a role in inducing ischemia reperfusion injury in post cardiac surgery patients.

The REFRESH I Clinical Study (see Investigator Brochure), using CytoSorb®, showed considerable reductions in both C3a and C5a complement components in subjects undergoing elective valve replacement and other cardiac surgeries, relative to control patients.

This proposed pivotal study will assess whether the CytoSorb® Device (a non-pyrogenic, sterile, single-use device designed to remove plasma free hemoglobin and other inflammatory mediators) can decrease the incidence or severity of AKI, as defined by KDIGO, when used intraoperatively with CPB in subjects undergoing cardiac surgery. An assessment of renal function characteristics will be made during post-cardiac surgery days 1-2 immediately following surgery and will examine use of an adjunctive therapy for decreasing cardiovascular surgery renal injury leveraging the established features of the CytoSorb® hemoadsorptive device, specifically through adsorption of inflammatory mediators including pfHb and complement.

The primary objective of the study outlined in this protocol will be to examine the ability of treatment with CytoSorb® to produce a decrease in the proportion of subjects with AKI. As secondary endpoints, this study will assess whether treatment with CytoSorb® can decrease the incidence of patients with worsening renal function as reflected by an increase in serum creatinine relative to their pre-surgical baseline, and the ability of CytoSorb® to remove significant amounts of pfHb and alternative complement pathway inflammatory mediators (C3a, C5a) during cardiac surgery requiring CPB. The demonstration of effective removal of hemoglobin and activated compliment will be assessed for their relationship to a reduction in post-operative complications and preservation of kidney function.

The REFRESH I study indicated that the valve replacement sub-population showed the strongest trend for a device mediated reduction of pfHb concentration (see Investigator Brochure). An analysis of the primary subgroup, patients undergoing valve replacement with another procedure, relative to the entire study population will be conducted to confirm this during the run-in phase of this adaptive trial.

In REFRESH I two CytoSorb® devices were introduced in parallel 1 hour after the start of CPB. In REFRESH II, we are proposing to introduce the devices sequentially with the first device starting at T=0 (start of CPB) and the second device starting at T= 90 minutes after start of CPB. Reduction of pfHb for both the 1 hour delayed introduction of CytoSorb® (REFRESH I procedure) and the sequential introduction of CytoSorb® (REFRESH II procedure) at time 0 and 90 minutes after start of CPB has been modeled in *in-vitro* testing (see Investigator Brochure). In both the 1 hour delayed CytoSorb® introduction post start of CPB (REFRESH I procedure), and the sequential introduction of CytoSorb® at time 0 and 90 minutes (REFRESH II procedure) after start of CPB, both device configurations perform equivalently with regard to pfHb reduction. In both experiments, hemoglobin (Hb) was infused over the duration of the experiment; therefore, any difference between the control and treatment groups demonstrates the effect of CytoSorb® to remove pfHb. The result of the *in-vitro* testing demonstrates that the CytoSorb® device can effectively remove hemoglobin from blood. Initiation of hemofiltration at the start of CPB will allow for the adsorption of potentially nephrotoxic inflammatory mediators from the onset of bypass.

#### 5. POTENTIAL RISK/BENEFIT

#### 5.1 Potential Investigational Device Benefit

The observed and potential benefits of using CytoSorb® device intraoperatively during CPB in cardiac surgery:

- Reduction of free hemoglobin generated as a result of the CPB procedure
- Reduced inflammatory burden generated during the CPB procedure via reduction in C3a and C5a
- Potentially, a decrease in worsening renal function in subjects at significant risk
- Potentially, a reduction in vasopressor requirements
- Possible decrease in the amount of time on a mechanical ventilator
- Possible decrease in hospital stay, post CPB, including time in ICU
- Reduced risk of systemic inflammatory response syndrome (SIRS)

### 5.2 Investigational Device Residual Risks

A risk analysis was performed per ISO 14971, Medical devices -- *Application of risk management to medical devices, to determine the risks associated with CytoSorb*®. The risk profile associated with the CytoSorb® is expected to be minimal and consistent with other extracorporeal treatments currently in clinical use, such as dialysis. These risks include:

- Removal of drugs and hormones
- Allergic response to device materials
- Reduction in platelet count
- Reduction in white blood cell count
- Reduction in proteins (albumin, total protein) which may increase with CPB duration
- Reductions in albumin may result in a reduction in serum calcium
- Coagulation within device
- Infection
- Blood loss
- Hypothermia and chills
- Hemolysis
- Device leakage
- Circuit leakage

• Death

### 5.3 Risk Mitigation/Risk Benefit Rationale

To evaluate device related risk, a risk analysis was performed in accordance with the harmonized International standard EN ISO 14971:2012 "*Medical devices - Application of risk management to medical devices*". The results of the analysis indicate that all potential device-related hazards have been reduced to an acceptable level. Mechanical and performance concerns have been reduced by extensive human, animal, and bench testing. The device materials have been shown to be biocompatible and acceptable for human use through ISO10993 testing and prior human clinical studies of the device for removal of beta-2 microglobulin in end-stage renal disease subjects and removal of cytokines in the treatment of sepsis. The CytoSorb® 300-ml Device has CE Mark approval as an extracorporeal cytokine filter and is believed to pose little or no additional risks relative to commercialized blood filter and dialysis devices.

All attempts will be made to minimize the clinical risks associated with the procedure. Adherence to protocol will be stressed by CytoSorbents' personnel during in-service training. All subjects will be monitored per routine standard of care. Based upon a re-analysis of data from the REFRESH I study (see Investigator Brochure) decreases in serum albumin and total serum calcium may be observed in the study population. Therefore, serum albumin, total serum calcium, and ionized calcium will be assessed pre-procedure; hourly for the duration of CPB; at the end of CPB; at admission to the post-surgical care unit and during post-operative Day 1. Administration of fluids (i.e. crystalloids) will be recorded pre-procedure, during the surgical procedure and following surgery through the end of the first post-operative day. Likewise, the supplementation of albumin and calcium will be recorded during the surgical period and following surgery through the end of the first post-operative day.

Treatment with CytoSorb® was well tolerated in the REFRESH I trial (see Investigator Brochure). This trial achieved the primary safety endpoint of the study with a favorable adjudication of all serious adverse events. There were no significant differences in the rates of adverse events (AEs) or serious adverse events (SAEs) between the two groups, including 30-day mortality, and there were no unanticipated adverse device effects (UADEs) reported.

AEs specifically related to the investigational device were infrequent (i.e., involving 2 [8.7%] subjects in the Treated arm with thrombocytopenia) and in both instances the subjects recovered without sequelae. The most frequent SAEs (occurring in  $\geq$  2 subjects in either treatment arm) were atrial fibrillation, thrombocytopenia, coagulopathy, anemia, anemia postoperative, pleural effusion, hypotension, malnutrition, and acute kidney injury. There were no appreciable differences in the frequency of SAEs between treatment arms.

Additionally, the Data Monitoring Committee (DMC) will be reviewing safety information on an ongoing basis, and this will also provide an additional level of risk mitigation.

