### 2.1 Summary of Previous Clinical Experience Informing Study Design:

CytoSorbents conducted REFRESH I, a prospective, randomized, controlled safety trial enrolling a small heterogeneous population, at eight major U.S. cardiac surgery centers to evaluate the safety and feasibility of CytoSorb®, a blood purification technology designed as an adjunctive therapy to remove inflammatory mediators (i.e., pfHb, activated complement and cytokines) in high risk cardiac surgery patients aged 18-80 years of age, where cardiopulmonary bypass (CPB) was expected to exceed 3 hours. Subject assessments were performed until subjects were discharged from the ICU. Subjects were monitored for AEs through 30 days after the procedure.

This trial achieved the primary safety endpoint of the study with a favorable adjudication of all serious adverse events. There were no significant differences in the rates of adverse events (AEs) or serious adverse events (SAEs) between the two groups, including 30-day mortality, and no unanticipated adverse device effects (UADEs) were reported. Three subjects (1 Control; 2 Treated) died of AEs that were considered by the Independent Physician Adjudicator to be not related to the device. Most AEs were related to the pre-existing conditions or to surgical procedures. AEs specifically related to the investigational device were infrequent (i.e., involving 2 [8.7%] subjects in the Treated arm) and in both instances the subjects recovered without sequelae.

A detailed description of the REFRESH I study results along with subsequent safety analyses of REFRESH I data; safety information derived from clinical applications other than CPB; and supporting preclinical assessments may be found in the Investigator Brochure. The investigator should read and understand the Investigator Brochure and use it in conjunction with this protocol in the evaluation of risk and benefit for patients being considered for enrollment into this study.

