### 2.2 REFRESH II Study design:

The REFRESH II study is designed to assess the intraoperative use of the CytoSorb® device in patients with an increased risk of acute renal failure following open heart surgery to decrease the circulating presence of nephrotoxic agents (such as pfHb, cytokines, and activated compliment during CPB) in conjunction with standard of care treatment. The study aims to determine whether the use of the CytoSorb® device can decrease the incidence or severity of AKI in the 48 hours immediately following surgery. This will be evaluated in a patient population that has been enriched for increased risk of cardiac surgery associated AKI and for procedures associated with a higher risk for pfHb generation.

In this study, creatinine and urine output collection will be used to identify acute kidney injury (AKI) as defined by the KDIGO clinical practice guidelines. This identification will be augmented through the use of additional indicators of renal damage and dysfunction, including assays for urinary TIMP2 and IGFBP-7 and serum elevations in HMGB1 and Cystatin C.

The CytoSorb® device that will be utilized in this randomized and blinded trial is based on size adsorption filtration. Each CytoSorb® adsorber cartridge contains micro-porous, polystyrene bead technology. Earlier in vitro and in vivo studies have shown this to correlate with the removal of endogenous mediators of inflammation and pfHb. This product, approved under a CE mark in Europe and other countries has been used in over 25,000 critical care cases, including about 6,000 cardiac surgery cases. It is believed that the removal of these renal-toxic substances from patient blood during surgery will lead to an overall reduction in kidney dysfunction among the patients who assigned to the treatment group relative to those who will be on standard of care alone.

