6.8.1 Primary Safety Endpoint

The primary safety endpoint of this trial is to evaluate the product safety profile through the assessment of device related adverse events during the study period.

There is no formal hypothesis associated with the primary safety endpoint. Device related adverse events will be tabulated with the number of events and subjects with event for each MedDRA (Version 21.0) SOC/preferred term and overall. Rates will be reported as the number of subjects who experience at least one event out of the total number of subjects.

| Statistical Analysis Plan Pa | | ge 15 of 19 | |
|------------------------------|---|-------------|---------|
| Sponsor | Study | | Version |
| CytoSorbents | CYTOSORB [®] REDUCTION OF FREE HEMOGLOBIN/ACU INJURY (AKI) DURING CARDIAC SURGERY | te Kidney | 1.0 |

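### Safety is half of the primary objective, but the SAP reports it without any interval or between-arm estimate, so the stopped trial cannot say how large an excess of serious harm it excludes

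*Protocol*

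**What the plan says.** The study objectives (Protocol 6.1.1 and SAP 3) are to evaluate both the safety and the performance of the device. Protocol 11.1.1 describes safety summaries by treatment group and leaves further detail to the SAP.

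SAP 6.8.1 says "There is no formal hypothesis associated with the primary safety endpoint". It tabulates device-related adverse events as numbers of events, numbers of subjects and simple rates. SAP 6.8.6 treats all adverse events, serious events and non-serious events in the same way, and lists deaths. Under SAP 6.1.1 and 6.2 these tables are shown by treatment group, with roll-in subjects in parallel. The only confidence intervals named anywhere in the SAP are those for the AKI subgroup odds ratios in 6.9.

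SAP 6.8 also defines relatedness. Its list of relationship grades that make an event device related (and, separately, procedure related) includes the grade unrelated.

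As background, Protocol 2.1 calls the previous study a "safety trial enrolling a small heterogeneous population" and reports that "Three subjects (1 Control; 2 Treated) died of AEs", adjudicated as not device related. Protocol 5.3 says "There were no significant differences in the rates of adverse events (AEs) or serious adverse events (SAEs) between the two groups, including 30-day mortality" and adds "There were no appreciable differences in the frequency of SAEs between treatment arms".

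**The concern.** A table of counts shows what was observed. It does not show what the data rule out. With no safety hypothesis, an interval is the only way for the report to say how large an excess of harm remains compatible with the results. The SAP was written after the decision to stop, when it was known that the sample would be far below the 420 planned, so the omission matters more than it would have at full size.

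The device-related rate in 6.8.1 has a further limit. Protocol 8.5.3.2 gives controls standard bypass, so that rate has little meaningful concurrent comparator. The comparison that randomisation does support is of events counted regardless of attribution, and no between-arm estimate is planned for it.

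At stake is whether the final report can answer the safety half of its objective.

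**Working it through.** **Inputs from the documents**
- 151 enrolled including roll-ins (SAP 4.1); number randomised not stated.
- Up to 80 roll-ins (Protocol synopsis, Sample Size). All receive the device (Protocol 6.2, SAP 4), and those in whom treatment was attempted belong to the Safety population (SAP 6.2).
- 1:1 allocation (SAP 4.2); two-sided 0.05 as the default test level (SAP 6.1.4).

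**Assumptions**
- Control event rates are in neither document; 10% to 40% is used as a range.
- Every enrolled subject who is not a roll-in is taken as randomised and treated. Enrolment means signed consent (Protocol Table 1), so true arm sizes could be smaller.

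**Step 1. Reproduce the one safety rate the protocol gives.** Protocol 5.3 reports device-related events "involving 2 [8.7%] subjects in the Treated arm with thrombocytopenia". The only whole-number denominator between 10 and 59 that gives 8.7% is 23 (2/23 = 8.70%). The exact (Clopper-Pearson) 95% interval for 2/23 is 1.1% to 28.0%. This shows how much a bare rate from a small arm conceals.

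**Step 2. Arm sizes in REFRESH II.**
- 80 roll-ins: (151 − 80)/2 = 35.5, about 36 per arm.
- No roll-ins: 151/2 = 75.5, about 75 per arm.

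**Step 3. Chance of missing a true doubling.** Exact enumeration of two binomials, two-sided 0.05 Fisher test. The SAP plans no such test for safety; it is used only as a yardstick for the information available.

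| Control to CytoSorb rate (assumed) | 36 per arm | 75 per arm |
|---|---|---|
| 10% to 20% | 86% | 68% |
| 20% to 40% | 63% | 29% |
| 30% to 60% | 36% | 4% |
| 40% to 80% | 9% | 0.1% |

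**Step 4. What an interval would say if the two observed rates were equal.** Approximate 95% half-width of the risk difference = 1.96 × √(2p(1 − p)/n).
- p = 10%: 1.96 × √(0.18/36) = 13.9 percentage points; 1.96 × √(0.18/75) = 9.6.
- p = 20%: 1.96 × √(0.32/36) = 18.5 percentage points; 1.96 × √(0.32/75) = 12.8.

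So identical observed rates of 10% would still leave an excess of about 10 to 14 points unexcluded.

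**Step 5. Zero events among device-treated patients.** Upper limit of the two-sided exact 95% interval = 1 − 0.025^(1/n). Roll-ins must be counted, because they receive the device.
- 36 randomised + 80 roll-ins = 116: 1 − 0.025^(1/116) = 3.1%.
- 75 randomised + 0 roll-ins = 75: 1 − 0.025^(1/75) = 4.8%.

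**The case against.** **Descriptive safety tables are a legitimate choice.** The SAP plans no safety test and no statement of no difference. Its tables are by arm, so an observed doubling would be visible. This stands: the gap is the missing measure of uncertainty, not concealment. A reader might infer that a doubling of harm would be reported as no difference, but nothing in the SAP says so. The sentence about non-significance in Protocol 5.3 describes the previous trial.

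**The safety argument has other supports.** A reader might also infer that the safety case rests on that trial. The documents do not support this. Protocol 5.3 cites a formal risk analysis ("The results of the analysis indicate that all potential device-related hazards have been reduced to an acceptable level"), biocompatibility testing, CE marking and monitoring committee review. Protocol 2.2 says the product has been "used in over 25,000 critical care cases, including about 6,000 cardiac surgery cases". Detailed results are referred to the Investigator Brochure, which is not among these documents. Rewording 5.3 would change nothing in a trial that has already stopped.

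**The size depends on the base rate.** This also stands. With common events a doubling would usually be detected, so the trial is not uninformative about every doubling.

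**An interval on a faulty numerator is of no use.** Correct. While SAP 6.8 counts unrelated events as device related, an interval in 6.8.1 would not describe device harm. That is a reason to correct the definition first. Intervals for serious events and deaths regardless of attribution do not depend on it.

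**Conclusion.** The point holds as a gap in the SAP's safety reporting. The final analysis of a trial with safety in its primary objective gives no interval or between-arm estimate for any safety outcome, and so cannot state the excess harm it excludes. At 36 to 75 per arm that excess is not small. For assumed control rates of 10% to 20%, a doubling would be missed between 29% and 86% of the time by a conventional test. Zero events among device-treated patients would leave a rate of about 3.1% to 4.8% possible.

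These figures rest on assumed control rates, an unstated number of roll-ins, and all enrolled subjects who are not roll-ins being randomised and treated. The lack of intervals rests on none of these. The change should be made: it is inexpensive and bears directly on what the report can conclude.

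**What to change.** 1. **SAP 6.8, first:** correct the relatedness definitions so that events rated unrelated are not counted as device related or procedure related.
2. **SAP 6.8.1:** add exact (Clopper-Pearson) 95% intervals for device-related event rates in CytoSorb-treated patients, with randomised and roll-in patients shown separately.
3. **SAP 6.8.6:** add the CytoSorb-minus-SoC risk difference with a 95% interval, among randomised treated patients and regardless of attributed relationship. Cover any serious event, death, and those events in Protocol 8.8.3 that can occur in both arms (for example platelet reduction, infection and blood loss). Leave out device-only events such as leakage of, or coagulation within, the device.
4. State that safety conclusions will cite the interval limits.

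The cost is a few columns in tables already planned, plus short SAP wording; no new data are needed. The downside is that the intervals will be wide and look less favourable than bare rates.
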